## **9 General Specifications for Data Analyses**

### **Data Handling After Cutoff Date**

Data after the cutoff date do not undergo the cleaning process. The only exceptions are the date of death and the date last known to be alive from the “End of Assessment Visit” in eCRF.

Data other than the date of death and the date last known to be alive obtained after the cutoff will not be displayed in any listings or used for summary statistics, e.g., laboratory values of samples taken after data cutoff, AEs with onset date after data cutoff, etc. will not be included in any analysis or listing.

### **Significance Level**

When CIs are to be calculated, these will be two-sided, with a confidence probability of 95%, unless otherwise specified in this IAP. For continuous data, CIs for the mean will be calculated assuming a normal distribution of the data. CIs for binary endpoints will be presented using the Clopper-Pearson method. All statistical tests mentioned in this IAP are to be regarded as exploratory. The significance level is 5% two-sided. If p-values are to be presented for descriptive purposes, it will be indicated with the statement that no inferential conclusion should be drawn from the p-value.

### **Presentation of Continuous and Qualitative Variables**

Continuous variables will be summarized using descriptive statistics, i.e.:

- number of patients, number of patients with non-missing values, number of patients with missing values,
- mean, SD,
- median, 25th Percentile-75th Percentile (Q1-Q3),
- minimum and maximum.

If there are no missing values, this will be indicated by a 0.

Qualitative variables will be summarized by counts and percentages.

Unless otherwise stated, the calculation of proportions will be based on the number of patients in the analysis population of interest. Therefore, counts of missing observations will be included in the denominator and presented as a separate category.

In cases where the analysis refers only to certain visits, percentages will be based on the number of patients still present in the study at that visit, unless otherwise specified.

### **Time-to-Event Data**

Time-to-event data will be summarized descriptively as continuous data and using Kaplan-Meier (KM) analysis. Data summarization will include:

- Plot of the KM curve with the number of patients at risk

- KM estimates with CI at fixed timepoints (e.g., every 6 months) (with number at risk/failed)
- Median survival times with CI, and the first quartile (Q1) and third quartile (Q3).

### **Definition of Baseline**

Data entered during the baseline visit are considered baseline data for the purposes of analysis; the last value before study treatment initiation will be considered the Baseline value. Baseline PROs can be filled out up to 7 days after the baseline visit. Baseline PRO scales will be completed before the first cladribine tablet dose is taken. Baseline MRI corresponds to the most recent MRI prior to starting cladribine tablets, which is expected to have been taken within the prior 90 days.

### **Definition of Change from Baseline**

*Change from baseline = visit value – Baseline value*

*Percent change from Baseline = 100 \* (visit value – Baseline value) / Baseline value*

### **Definition of Duration**

Duration will be calculated by the difference of stop and start date + 1 (if not otherwise specified).

The time since an event (e.g., time since first diagnosis) will be calculated as reference date minus date of event.

### **Conversion Factors**

The following conversion factors will be used to convert days into months or years:

*1 month = 30.4375 days, 1 year = 365.25 days.*

### **Handling of Missing Data**

Unless otherwise specified, missing data will not be replaced.

Missing statistics, e.g., when they cannot be calculated, should be presented as “nd.” For example, if n=1, the measure of variability SD cannot be computed and should be presented as “nd.”

Where tables are presented over time, the total of missing and non-missing observations at each timepoint should reflect the population still in the study at that time. For example, if a patient is still in the study at the timepoint but with missing data, it should be counted in the number of missing observations.

For PRO items with missing responses, the response will be managed as described in Sections 16.3 and 16.4.

### **Handling of Partially Missing MS Onset (First Attack), MS Diagnosis, or Prior DMD Medication Dates**

For time since MS onset, MS diagnosis, or prior DMD start dates, a missing onset day/month will be replaced by 1 for the duration derivation or the derivation of DMDs used within

24 months prior to study start. For determination of whether a DMD was used within 24 months of study start, the missing ending day/month of DMD use will be replaced by the end of the month if day is missing, or December 31, if both a day and a month are missing. If the imputed partial dates will result in an ending date for the last DMD on or after the date of the first dose of cladribine, then the partial dates will be re-imputed to the date corresponding to the day before the first dose of cladribine.

### **Handling of Partially Missing Dates for Relapse Onset and Stabilization and for First Attack**

To identify relapses in the past 2 years, a missing day/month for the onset date will be replaced by 1, while a missing ending day/month for the stabilization will be replaced by the end of the month, if day is missing, or December 31, if both a day and a month are missing. A missing day/month of the first attack date will be replaced by 1.

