### **ARR (Retrospective Data)**

The ARR based on the last 24 months prior to the start of treatment with cladribine tablets will be assessed. The retrospective 24-month ARR for a patient is calculated as:

*(No. of relapses within 24 months prior to written informed consent for that patient / [30.4375\*24]) \* 365.25*

For patients diagnosed with MS at least 12 months but less than 24 months prior to written informed consent, the number of relapses since MS diagnosis will be used, and the ARR calculation will be as follows:

*(No. of relapses since MS diagnosis and prior to written informed consent for that patient / [Informed consent date - Initial MS diagnosis date]) \* 365.25*

Such a variable will be summarized descriptively.

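### Partly missing relapse and diagnosis dates go to the earliest possible day, and the SAP does not say whether onset or overlap places a relapse in the 24-month look-back window

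*SAP*

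**What the plan says.** SAP section 9 has two rules for partial dates that feed the retrospective ARR.

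- **Relapses.** The stated purpose is "To identify relapses in the past 2 years". For that purpose "a missing day/month for the onset date will be replaced by 1". Stabilization dates are treated the opposite way: the last day of the month stands in for an unknown day, and 31 December is used when the month is unknown too. Onset therefore goes to the earliest possible date and stabilization to the latest.
- **MS diagnosis.** The preceding rule says "a missing onset day/month will be replaced by 1 for the duration derivation". The SAP gives no other rule for partial diagnosis dates, so I assume this one also feeds the ARR.

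SAP section 11.3, ARR (Retrospective Data), has two formulas.

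- Diagnosis at least 24 months before consent: the numerator is "No. of relapses within 24 months prior to written informed consent for that patient" and the denominator is fixed at 24 months.
- Diagnosis 12 to under 24 months before consent: the numerator is "No. of relapses since MS diagnosis and prior to written informed consent for that patient" and the denominator is "Informed consent date - Initial MS diagnosis date".

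Neither section says whether onset or any overlap with the window makes a relapse count. Protocol section 9.3 asks sites to record relapses from the two years before the study period, or since diagnosis if that is more recent, with onset and resolution dates. No sensitivity analysis of the partial-date rules is planned.

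**The concern.** An earliest-date rule is not neutral when the date decides membership of a look-back window. A year-only relapse from the year in which the window opens is placed on 1 January, before the window starts, wherever in that year it occurred. Under protocol section 9.3 the site has already judged the relapse to be recent enough to record, so the rule can overrule the better information. For diagnosis dates, the rule lengthens time since diagnosis and can only move patients out of the under-24-month group, which is also a listed subgroup in SAP section 8.2.

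The retrospective ARR is a secondary objective and the natural reference for a reader of the on-treatment ARR. The prior-relapse count (at most 1 versus more than 1) adjusts the negative binomial and zero-inflated sensitivity models in SAP section 14.1, and the count enters the multiple-imputation model. Section 11.3 also summarises relapse duration. With the imputed dates and the SAP's stop minus start plus 1, a relapse with both dates known only to the same year lasts 365 days (366 in a leap year).

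**Working it through.** **Inputs.** The SAP gives "1 month = 30.4375 days, 1 year = 365.25 days". Protocol section 6 gives consent dates from 31 July 2019 to 28 November 2022. The minimum time since diagnosis is 12 months (protocol section 9.2.1). The documents give no share of partial dates and no expected retrospective ARR, so there is no plan figure to reproduce. The constants agree: 30.4375 × 24 = 730.5 days, and 365.25 / 730.5 = 0.5.

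**Assumptions.** Consent dates are uniform over the stated range, the relapse rate is constant, and diagnosis dates are uniform within 12 to 24 months before consent.

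**1. Year-only relapses, onset decides.** Let f be the fraction of the calendar year elapsed at consent. The window opens at the same fraction of the year two years earlier, so the part of that year inside the window is (1 − f) years out of 2. All of it is lost, so the lost share is (1 − f)/2.

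- Averaged over uniform f this is 1/4. Enumerated over the study's own consent dates it is 23.8%.
- By consent date in 2021: 47.9% on 15 January, 25.1% on 1 July, 2.2% on 15 December.
- Relapses dated to the two later calendar years stay in. No relapse from before the window is brought in, so nothing offsets the loss.
- If only the day is missing, the loss is 2.0%.

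Effect on the total count = share of relapses that are year-only × 23.8%:

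| Assumed year-only share | Change in count |
|---|---|
| 2% | −0.5% |
| 5% | −1.2% |
| 10% | −2.4% |
| 20% | −4.8% |
| 50% | −11.9% |

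**2. Year-only relapses, overlap decides.** With stabilization at 31 December, every relapse from the window-opening year overlaps the window, so none is lost. If sites recorded only in-window relapses, the effect is about nil. If they also recorded older ones, the count of year-only relapses rises by 26.2% (2.6% to 5.2% of the total at shares of 10% to 20%).

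**3. Year-only diagnosis, true time since diagnosis 12 to under 24 months.** The imputation adds 182 days on average and moves 47.8% of such patients to the 24-month formula. For example, with consent on 1 July 2021 and diagnosis on 1 October 2019, the true interval is 639 days. Imputed to 1 January 2019 it is 912 days, so the 24-month formula applies. One relapse since diagnosis then gives 0.50 instead of 365.25 / 639 = 0.57.

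The numerator window lengthens too, so the mean ratio of imputed to true ARR depends on what is counted in the added time:

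| Relapse rate counted before diagnosis, relative to after | Year-only | Day only missing |
|---|---|---|
| 0 (recorded only since diagnosis) | 0.82 | 0.97 |
| 1 | 1.00 | 1.00 |
| 2 | 1.18 | 1.03 |
| 4 | 1.54 | 1.08 |

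In the whole cohort this is small. If 10% of patients are in this group and 10% of those have a year-only date, the change is 0.10 × 0.10 × (−0.18) = −0.18%. At 20% and 30% it is −1.08%, taking their ARR as similar to the others'. Patients truly diagnosed 24 months or more before consent keep the 730.5-day denominator.

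**4. Mid-period imputation.** Counted over relapses at any time in the four years before consent, 1 July changes the year-only count by −1.4%, but only because false inclusions offset false exclusions. Of relapses truly in the window, a plain 1 July rule still drops about 7%. Bounding the date to the window where the site placed the relapse there drops none. For diagnosis, 1 July bounded by the 12-month criterion brings the first-row ratio from 0.82 to within about 3% of 1, with the count held fixed.

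**The case against.** The strongest reply is that the text fits an overlap reading at least as well. A stabilization date has no function in an onset-only test, yet the SAP imputes it for the same stated purpose. The rule for prior disease-modifying drugs pairs earliest start with latest end in the same way. On that reading no in-window relapse is lost. This stands, and it is why the point cannot be put as a demonstrated downward bias. It does not settle the matter, because the ARR formula leaves membership open and onset is the usual way to date a relapse.

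A reader might also infer that the diagnosis-date rule necessarily lowers the ARR. The documents do not support that. The numerator runs from the same imputed date, so the net effect depends on whether pre-diagnosis relapses are in the data. If sites follow protocol section 9.3 they should not be, and 0.82 applies. By the same logic the upward overlap figure then falls away. Assuming that sites record only in-window relapses for one figure and older ones for the other would be inconsistent.

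The size is also uncertain. The share of partial dates is unknown, the protocol asks for onset and resolution dates, and monitors check case report forms against patient records. The endpoint is descriptive with no planned pre/post test, and the covariate changes only if a patient crosses the cut. All of this stands and limits the point to a minor one.

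**Conclusion.** The concern holds in a limited form. The earliest-date rules are explicit and the membership criterion is missing. Two programmers could both follow the SAP and obtain different counts. If sites record only what was asked, the onset reading loses 23.8% of year-only relapses, the overlap reading loses none, and the affected recently diagnosed patients have an ARR ratio of 0.82. If older relapses are also recorded, the overlap reading gains 26.2% and the diagnosis effect can go either way.

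A reader might go further and conclude that the retrospective ARR is biased downward, or that year-only relapses in general fall out of the window. Neither follows. Only relapses from the window-opening calendar year are at risk, and only under the onset reading.

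At assumed year-only shares of 10% to 20% the count changes by −2.4% to −4.8% under onset. The figures rest on uniform consent and diagnosis dates, a constant relapse rate and an assumed share of partial dates. The consequence is a few percent on a descriptive secondary endpoint and some misclassification of a covariate in sensitivity models. The primary ARR is not affected.

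**What to change.** In SAP section 9, with a cross-reference in section 11.3:

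1. State that the onset date decides whether a relapse falls in the look-back window.
2. Impute relapse onset and MS diagnosis dates to the 15th when only the day is missing and to 1 July when day and month are missing, within known bounds. Onset is not after consent. Where the site recorded the relapse as within the prior two years or since diagnosis, onset is not before the window start. Diagnosis is at least 12 months before consent.
3. Do not compute relapse duration from a date with an imputed month.
4. Report the number of imputed onset and diagnosis dates, separately for day-only and for month and day.

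The bounds matter, since an unbounded 1 July rule would still drop about 7% of in-window year-only relapses. The cost is a few SAP sentences and a small programming change, plus reliance on the site's judgement that the relapse fell in the window.

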### **Time Window**

Day 1 is the day of the start of the study dose; the day before is Day -1 (Day 0 is not defined).

Study day / Study dose day is defined relative to Day 1.

Visits will be conducted within the context of routine clinical care; thus, the timing of study visits is approximate and not mandated by the study protocol. The PDSS and MS-TAQ will be analyzed according to the visit collected through the eCRF. For all the other PROs collected at Months 6, 12, and 24, the analysis windows are  $\pm$  1 month (30 days). The analysis windows for the different months will be derived considering Day 1 (day of start of study dose), regardless of possible treatment delays in the second year. Endpoints without an analysis window will be analyzed according to the visit collected through the eCRF (if available).

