Investigators are expected to assess patients' absolute lymphocyte count (ALC) in accordance with the USPI and to follow any other recommended monitoring and guidance as specified in the USPI. Based on this, investigators are expected to assess the ALC before initiating cladribine tablets in Year 1, before initiating cladribine tablets in Year 2, as well as 2 and 6 months after start of treatment in each treatment year or as clinically indicated. It is assumed that investigators will not exclusively assess the ALC, but rather the complete blood count (CBC) and, at some of these time points, also lymphocyte subsets and certain CCI [REDACTED] These data will be collected as available.

[figure not shown]
Patients with lymphopenia resulting in delay of the scheduled Year 2 treatment course are expected to receive the second treatment course once the lymphocyte count is appropriate (≥ 800 cells per microliter) consistent with USPI labeling and will be followed up until the end of the observation period. If the ALC drops to <500 cells per microliter, the patient should be actively monitored until values increase as per USPI. If the ALC drops to <200 cells per microliter, anti-herpes prophylaxis should be administered, and the patient should be monitored for infections. Such unscheduled additional hematology assessments as per clinical requirements should be documented as well.

An overview of the study design is shown in Figure 1.

Visits and assessments are detailed in the Schedule of Assessments (see Section 9.2.4).

¹ If Year 2 treatment is delayed, final follow up visit may occur at Month 30

Figure 1. Study Design Schematic

^a Duration between stopping previous oral or infusion DMD and start of cladribine tablets is at the discretion of the investigator.

^b YEAR 2 course may be delayed for some patients, according to the ALC. If Year 2 treatment is delayed, follow-up may continue through Month 30.

Note: Refer to Table 1 for more data collection details and assessments at each visit.

Company substance code: 700568
Protocol number: MS700568_0079

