In accordance with the USPI, it is anticipated that patients may not receive their second course of cladribine tablets precisely 12 months after the initiation of cladribine tablets owing to ALC levels <800 cells per microliter or other potential clinical factors. In the event that the second course of cladribine tablets is delayed beyond Month 13, the PRO only collection scheduled for Month 13 should be adjusted to occur during the start of the second course of cladribine tablets. The timing of Visit 4 (Month 14) and the subsequent visits may need to be adjusted based upon the actual start date of the second course of cladribine tablets, which will be recorded by the investigator.

Table 1. Schedule of Assessments

Assessments	Data collection time points (as expected based on routine clinical practice)									
	Pre-baseline Screening Visit	Baseline Visit ^a	PRO Only ^b	Visit #1	Visit #2	Visit #3	PRO Only ^b	Visit #4	Visit #5	Visit #6
(Days -60 to 0)	Month 0	Month 1	Month 2	Month 6	Month 12	Month 13	Month 14	Month 18	Month 24 ^j	
Informed consent	X									
Medical history, previous relapses, previous DMD treatment		X								
Inclusion / exclusion criteria	X									
Demographic data	X									
Pregnancy test, HIV, hepatitis B and hepatitis C and tuberculosis status		X				X				
Cladribine tablets ^c		X		X		X		X		
Other MS DMD during study period, if applicable				X		X		X		X
Neurological examination as per standard of care		X			X	X			X	X
Physical examination as per standard of care		X								
Relapse count (prospective) ^d						X				X
MRI documentation ^e		X			X	X			X	X
Hematology assessment (ALC, CBC, lymphocyte subsets, immunoglobulins) ^f		X		X	X	X		X	X	X
Patient-reported outcomes										
Treatment adherence ^g		X ^h	X	X			X	X		
TSQM		X ^h			X	X				X
SF-36		X ^h			X	X				X

Company substance code: 700568
Protocol number: MS700568_0079

^a Duration between end of previous treatment and start of cladribine tablets is at the discretion of the investigator.

^b At the PRO only time point, patients fill out the PROs at their home; patients do not come to the clinic for filling out PROs at these time points.

^c Cladribine tablets are expected to be taken according to the USPI. If cladribine tablets are discontinued, reasons for discontinuation and follow-up MS treatment will be collected.

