## 5 Objectives and Endpoints

Objectives	Endpoints (Outcome Measures)	Endpoints (Outcome Measures) Timeframe	IAP Section
Primary			
To estimate the annualized relapse rate (ARR) over a 24-month period in patients with Relapsing form of Multiple Sclerosis (RMS), including relapsing-remitting multiple sclerosis (RRMS) and active secondary progressive multiple sclerosis (aSPMS) who are treated with cladribine tablets in a real-world setting and after suboptimal response to any oral or infusion Disease-Modifying Drug (DMD) approved in the United States (US) for RMS	ARR over 24 months of treatment with cladribine tablets (prospectively collected data)	24-month period from first dose of cladribine tablets (or 30 months if Year 2 treatment is delayed)	Section 14.1
Secondary	
To assess Patient-Reported Outcomes (PROs), treatment adherence, and treatment satisfaction during treatment with cladribine tablets
 
Baseline scores, scores at the timepoints, and change in scores from Baseline to timepoints (Month 6, 12, and 24) for the following PROs (collected via electronic PRO [ePRO] at the practice or at the patient's home):
 

• 14-Item Treatment Satisfaction Questionnaire for Medication (TSQM)

• 36-Item Short Form Health Survey (SF-36)

• Modified Fatigue Impact Scale – 5-item version (MFIS-5)

• Beck-Depression Inventory – Fast Screen (BDI-FS) (7 items)

• Work Productivity Activity Impairment – Multiple Sclerosis (WPAI-MS) (6 items)

	24-month period from enrollment	Section 16.3 and Section 16.4

Objectives	Endpoints (Outcome Measures)	Endpoints (Outcome Measures) Timeframe	IAP Section
	
 
Patient Determined Disease Steps (PDDS) scale
 
 
Treatment adherence based on modified versions of the MS-TAQ; data to be collected via ePRO at Baseline (modified for once- or twice-daily oral dosing to assess adherence during last previous oral DMD treatment, or modified for infusion dosing to assess adherence to last previous infusion DMD treatment, only baseline scores) and at the end of Months 1, 2, 13, and 14 (modified for cladribine tablets, only scores at the different time points)
	Timepoints for TSQM, SF-36, MFIS-5, BDI-FS, WPAI-MS, and PDDS: Baseline, Months 6, 12, and 24 (or 30 months if Year 2 treatment is delayed) Adherence assessment timepoints: Baseline (adherence to previous DMD), Months 1, 2, 13, and 14 (adherence to cladribine)	

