## Overview of Planned Analyses

There will be a baseline analysis, 3 interim analyses, and a final analysis. Baseline and interim analyses are descriptive and for monitoring purposes. Multiplicity corrections will not be considered. Statistical analyses will be performed using the Electronic Case Report Form (eCRF) data gained until the cutoff dates described in the following subsections.

If the start of cladribine Year 2 treatment needs to be delayed (e.g., to allow for lymphocyte recovery to at least 800 cells/mL), all Year 2 visits and procedures will be moved out accordingly (at most 6 months). If recovery to 800 cells/mL is not complete after the 6-month delay, Year 2 treatment should not be initiated; the patient will nonetheless be followed up until the end of the observation period.

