### **6.5                    Final Analysis**

A final analysis will be performed on the 24-month data (or 30 months if Year 2 treatment is delayed) for all patients at the end of the study. The corresponding cutoff is expected by the end of March 2025.

The final analysis will include all the endpoint analyses related to the objectives of the study. For the PROs, the actual value at each visit and the change in scores from Baseline to Months 6, 12, and 24 will be considered. A comparison of the characteristics of patients who complete the study vs. those who drop out will be conducted as well.

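### The Month 24 window for five PROs stays fixed to Day 1 while the Year 2 visits move by up to 6 months, so completed final questionnaires from delayed patients usually fit no window

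*SAP*

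**What the plan says.** Four parts of the SAP bear on when the last PRO is collected and when it counts.

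- **Section 6 (Overview of Planned Analyses).** If the Year 2 course is delayed, "all Year 2 visits and procedures will be moved out accordingly (at most 6 months").
- **Section 5 (Objectives and Endpoints).** The timepoints for TSQM, SF-36, MFIS-5, BDI-FS, WPAI-MS and PDDS are "Baseline, Months 6, 12, and 24 (or 30 months if Year 2 treatment is delayed").
- **Section 6.5 (Final Analysis).** "A final analysis will be performed on the 24-month data (or 30 months if Year 2 treatment is delayed) for all patients".
- **Section 9 (Time Window).** PROs other than PDDS and MS-TAQ have windows of 30 days either side of Months 6, 12 and 24. Those windows "will be derived considering Day 1 (day of start of study dose), regardless of possible treatment delays in the second year". The other two follow a different rule: "The PDSS and MS-TAQ will be analyzed according to the visit collected through the eCRF" (PDSS is evidently PDDS).

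The protocol also allows for the shift. Section 9.1.1 places the Months 6, 12 and 24 PRO collection under a footnote: "If Year 2 treatment is delayed, final follow up visit may occur at Month 30". Section 9.2.4 says that Visit 4 and later visits may be re-timed to the actual start of the second course.

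**The concern.** Collection follows the second course, but the analysis window follows the first dose. For a patient whose second course is late by well over 30 days, the final questionnaire is due after the only late window has closed. No Month 30 window exists, and no rule reassigns a late assessment.

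Section 9 (Handling of Missing Data) states: "Unless otherwise specified, missing data will not be replaced". It also counts a patient who is still in the study without a value as missing. A delayed patient is still in the study at Month 24, so a completed questionnaire would be tabulated as missing for five instruments. PDDS from the same visit would be tabulated as Month 24, and the six PROs would then describe different populations under one label.

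The loss is also unlikely to be random. Protocol Section 9.2.4 attributes a late second course to factors "owing to ALC levels <800 cells per microliter or other potential clinical factors". The patients dropped would therefore be selected partly by slow lymphocyte recovery.

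**Working it through.** **Inputs**

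- Month length 30.4375 days (SAP Section 9, Conversion Factors).
- Day 1 is the first dose and there is no Day 0; window of 30 days either side of Months 6, 12 and 24 (SAP Section 9, Time Window).
- Maximum shift of 6 months (SAP Section 6).
- Visit scatter: **assumed** normal around the shifted date, SD 7, 15 or 30 days. The documents give no figure.

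**Step 1: the plan's own figure.** Month 24 + 6 months = Month 30, as in SAP Section 5. It reproduces.

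**Step 2: the windows.** Centre = months × 30.4375 + 1.

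- Month 12: 12 × 30.4375 + 1 = 366.25, so Days 336.25 to 396.25.
- Month 24: 24 × 30.4375 + 1 = 731.5, so Days 701.5 to 761.5. SAP Section 14.1.1 uses the same 731.5 as its 24-month bound for time on study.

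No window opens after Day 761.5. Other day counts change little: without the Day 1 offset the Month 24 window is 700.5 to 760.5, and with 30-day months it is 690 to 750.

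**Step 3: where a shifted final PRO falls.** Day = 731.5 + delay.

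- 31 days: 762.5, which is 1.0 day past the window.
- 60 days: 791.5, which is 30 days past.
- 6 months: 30 × 30.4375 + 1 = 914.1, and 914.1 − 761.5 = 152.6 days past.

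**Step 4: allowing for approximate visit dates.** Probability of falling outside Days 701.5 to 761.5:

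| Delay (days) | SD 7 | SD 15 | SD 30 |
|---|---|---|---|
| 31 | 0.557 | 0.527 | 0.534 |
| 45 | 0.984 | 0.841 | 0.698 |
| 60 | 1.000 | 0.977 | 0.843 |
| 91 | 1.000 | 1.000 | 0.979 |
| 182.6 | 1.000 | 1.000 | 1.000 |

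**Step 5: is another collection due near Day 731?** Protocol Section 9.1.1 schedules these PROs only at Months 6, 12 and 24. After a full 6-month shift, the visit landing near Month 24 is the nominal Month 18 visit (18 + 6 = 24), which is not one of those timepoints.

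**Step 6: how many patients.** The share delayed is not given. For illustration only, suppose delays are uniform over 0 to 6 months. Then 1 − 30/182.625 = 84% of delayed patients have a nominal date past the window. If 5% to 25% of patients were delayed, that is about 4 to 21 per 100 patients.

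**The case against.** The Day-1 clock is explicit and addresses delay directly, so it reads as a deliberate choice to analyse by time since first dose. The endpoint definitions speak of change to Months 6, 12 and 24, never of a Month 30 change score. That is a legitimate estimand. It still leaves the Month 24 cell empty for a shifted assessment, because nothing else is collected near Day 731, and it does not fit the timepoints in SAP Sections 5 and 6.5.

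The protocol wording is permissive and the ePROs can be completed at home, so some delayed patients may answer near Month 24. This stands, and the probabilities above apply only where the PRO moves with the visit. SAP Section 6, however, says the visits will move.

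No sentence says out-of-window PROs are discarded, and the SAP sends endpoints without a window to the eCRF visit. That fallback does not reach these five, which do have windows.

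PDDS is also recorded on a running page (Protocol Table 1, footnote i), which partly explains its separate handling but not the differing populations.

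The size is uncertain: the visit SDs and the share delayed are assumptions. With a last visit planned for 03-Jan-2025 (Protocol Section 6), patients first dosed after about early July 2022 cannot reach Month 30. No link between delay and PRO scores is shown either; non-random loss is plausible, not demonstrated. All of this limits the size and leaves the conflict in place.

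A narrower repair, keeping the Day-1 windows and adding a final-assessment row for delayed patients, would also avoid losing data.

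**Conclusion.** The concern holds. SAP Sections 5, 6 and 6.5 move the last PRO to as late as Month 30, while Section 9 accepts five of the six PROs only up to Day 761.5. At about 31 days of delay roughly half of the shifted assessments miss the window (53% to 56%). At 45 days 70% to 98% miss it, at 60 days 84% to 100%, and at 6 months all of them. These figures assume that the PRO moves with the visit and that visit dates scatter with an SD of 7 to 30 days. The total number of patients lost cannot be computed from the documents.

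The effect is on the completeness and interpretation of descriptive secondary endpoints. No test and no part of the primary ARR analysis is affected. It should be corrected before the final tables are produced.

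**What to change.** - In SAP Section 9, analyse the final assessment of TSQM, SF-36, MFIS-5, BDI-FS and WPAI-MS by eCRF visit, the rule already used for PDDS and MS-TAQ. It needs no Year 2 start date, so it is also defined for patients who never begin the second course.
- Keep the Day-1 window of 30 days either side as a sensitivity table.
- Report how many final assessments fall outside Days 701.5 to 761.5, with the median and range of time since first dose.
- Reconcile SAP Sections 5, 6 and 9 so that all three state the same rule, consistent with Section 6.5.

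The cost is one sentence in the SAP, one programming change and one extra table, with no new data. The drawback is that the Month 24 label then covers a range of times since first dose, up to about Month 30. A footnote to the table should say so.
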